8.1.2 Geometric Mean Titer

For the ALS titer, antibody levels will be summarized on the original scale by treatment group at Screening, Day 7 and Day 19. The number of observations, geometric mean titer (GMT) and geometric 95% CI of the GMT will be reported. For ALS titers reported as below the assay Lower Level of Quantification (LLoQ), a value of half of the LLoQ will be used. The GMT will be calculated as the antilog of the mean of the logarithms of the ALS titer. The 95% CIs of the GMT will be based on the t-distribution to provide population estimates and will be presented as the antilog. Two-sided 95% CIs for the ratios of post dose 1 and post dose 2 GMTs between two treatment groups will be constructed using the log normal distribution. The log values will be used to construct a CI using the t-distribution for the mean difference between all

pair-wise comparisons. The mean difference and the corresponding CI limits will then be exponentiated to obtain the GMT ratio and the corresponding CI. Each pairwise comparison will be performed on the lognormal assay responses using a t-test. If the values deviate from the log normal distribution, a non-parametric method (i.e., Wilcoxon) may be used for the analysis of the ratio of GMT.

Tables 14.2.3.1 (a)(b)(c)(d) - 14.2.3.2 (a)(b)(c)(d) will summarize the GMTs and 95% CIs for each antigen and treatment group for the FA population and the PP population, respectively. The ratio of GMTs, 95% CI of ratio of GMTs and t-test will be summarized in Tables 14.2.4.1 (a)(b)(c)(d) - 14.2.4.2 (a)(b)(c)(d). Reverse cumulative distribution curves for the ALS titer after the first vaccination (Day 7) and the second vaccination (Day 19) will be presented by treatment group for each antigen analyzed as depicted in Figures 14.2.5.1 (a)(b)(c)(d) - 14.2.5.2 (a)(b)(c)(d).

8.1.3 Geometric Mean Fold Rise

For the ALS titer, the fold rise will be calculated after the first vaccination (post vaccination 1 antibody titer/baseline antibody titer), after the second vaccination (post vaccination 2 antibody titer/baseline antibody titer), and after the second vaccination compared to first vaccination (post vaccination 2 antibody titer/post vaccination 1 antibody titer). The number of observations, GMFR and 95% confidence intervals for the GMFR will be reported. The GMFR will be calculated as the antilog of the mean of the logarithms of the calculated fold rise. The 95% CIs for the GMFR will be based on the t-distribution to provide population estimates and will be presented as the antilog. Pairwise comparisons of the logs of the fold-rise will be performed using a t-test. If the values deviate from the log normal distribution, a non-parametric method (i.e., Wilcoxon) may be used for the analysis of the fold rise.

Tables 14.2.6.1 (a)(b)(c)(d) - 14.2.6.2 (a)(b)(c)(d) will summarize the GMFRs and 95% CIs for the GMFRs for each antigen and treatment group for the FA population and the PP population, respectively. In addition, the p-value from a t-test for each treatment group comparison will be presented for each time period and antigen as shown in Tables 14.2.7.1 (a)(b)(c)(d) - 14.2.7.2(a)(b)(c)(d) for the FA population and the PP population, respectively.

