5 SAMPLE SIZE CONSIDERATIONS

The sample size for this study was selected to detect frequent adverse events. Given a planned sample size of groups of 15 adults, toddlers, and younger children each receiving one of varying dose levels of ETVAX with or without dmLT, the study will have an approximately 80% and 90% chance of observing at least one serious adverse event or adverse event of special interest for events that occur at a rate of 10.3% and 14.3%, respectively. Additionally, if no serious adverse events are observed in 15 participants, the upper bound of the one-sided 95% confidence interval on the rate of serious adverse event occurrence is approximately 18%.

For infant cohorts with 30 participants per dose group, the study will have an approximately 80% and 90% chance of observing at least one serious adverse event or adverse event of special interest for events that occur at a rate of 5.3% and 7.4%, respectively. If no serious adverse events are observed in 30 participants, the upper bound of the one-sided 95% confidence interval on the rate of serious adverse event occurrence is approximately 9.5%.

For infant cohorts, with 30 participants per group, this study is designed to provide approximately 73% power to detect as low as a 2-fold difference in geometric mean fold rise (post-vaccination / baseline) between comparisons of two groups with varying doses of ETVAX and dmLT levels. This power calculation was based on the variability estimate, log10 standard deviation of 0.6, for CS6 obtained from a previous study of the vaccine in Sweden (VAC 003/OEV-121) and two-sample t-test using the 5% two-sided Type I error rate and 10% drop-out rate.

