6.4 Covariates and Subgroups

There is no a priori plan to summarize the immunogenicity or safety endpoints for covariates. The protocol is set up as a descending age-group study, so each age-group will be summarized separately. The 4 age groups to be analyzed are adults, toddlers (24-59 months), younger children (12-23 months), and infants (6-11 months). The protocol does not define any additional subgroup analyses.

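### Comparing arms on log post-dose titre adjusted for log baseline titre would be a cheap improvement on the two separate t-tests planned, and would give one ratio with a confidence interval

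*SAP*

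**What the plan says.** Section 8.1.2 (GMT, ALS): "Each pairwise comparison will be performed on the lognormal assay responses using a t-test". Section 8.1.3 (fold rise, ALS): "Pairwise comparisons of the logs of the fold-rise will be performed using a t-test". Sections 8.2.2 and 8.2.3 (fecal) and 8.3.2 and 8.3.3 (plasma) repeat the pair, with a Wilcoxon test as a possible substitute. Section 6.4 rules out covariates: "There is no a priori plan to summarize the immunogenicity or safety endpoints for covariates".

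The GMT comparison shells (Table 14.2.3.1) show a ratio, its 95% CI and a p-value. The fold-rise comparison shells (Table 14.2.6.1) show p-values only. Section 5 nevertheless sizes the infant groups for "approximately 73% power to detect as low as a 2-fold difference in geometric mean fold rise".

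Section 6.3.4 makes the per-protocol (PP) population primary for immunogenicity and requires a baseline result for the sample and antigen concerned. Section 6.3.3 admits participants with only a pre- or only a post-vaccination result to the Full Analysis (FA) population.

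**The concern.** Both planned tests address whether one arm responds more than another, and each makes a fixed choice about baseline: a slope of 0 for GMT, a slope of 1 for fold rise. If the true slope lies between, a baseline imbalance between arms pushes the two results in opposite directions. Holm is applied within each endpoint (Section 6.8), so both results can be flagged as significant or not, and nothing says which one governs. Estimating the slope generally gives a more precise comparison than fixing it, and a single answer. It needs only a measurement the trial already takes. The contrast used for sample size also never appears as an estimate with an interval.

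**Working it through.** **Inputs from Section 5.** Effect: 2-fold, so log10(2) = 0.301. SD: "log10 standard deviation of 0.6, for CS6 obtained from a previous study of the vaccine in Sweden"; the text does not say whether this is the SD of titre or of fold rise, and it is read first as fold rise. Test: "two-sample t-test using the 5% two-sided Type I error rate and 10% drop-out rate". Size: "For infant cohorts, with 30 participants per group", so 30 × 0.9 = 27. Not in the SAP and assumed: the correlation r of log baseline with log post-dose titre, and equal SDs s at the two times.

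**The plan's own figure.** SE = 0.6 × √(2/27) = 0.163, and 0.301/0.163 = 1.84. Power is 44.0% (noncentral t) or 45.4% (normal), not 73%. Without dropout (30 per group) it is 48.1%.

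**The two estimates side by side.** On participants with both results, log GMT ratio − log GMFR ratio = log baseline ratio between arms, at any r. With true slope b and baseline imbalance d, the GMT comparison shifts by b·d and the fold-rise comparison by (b − 1)·d. With 15 per arm and an assumed baseline log10 SD of 0.3, 0.5 or 0.7, the SE of d is SD × √(2/15) = 0.110, 0.183 or 0.256. That is 1.3-, 1.5- or 1.8-fold, against a 2-fold target.

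**Power by method, 27 per group.** Var(fold rise) = 2s²(1 − r) = 0.6², which gives s. The residual SD after baseline adjustment is s√(1 − r²), with variance inflated by 1 + 1/(54 − 4) = 1.02 and one further degree of freedom lost.

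| r | s | GMT t-test | Fold-rise t-test | Adjusted | Variance vs fold rise, (1+r)/2 × 1.02 | Variance vs GMT, (1−r²) × 1.02 |
|---|---|---|---|---|---|---|
| 0 | 0.424 | 72.5% | 44.0% | 71.7% | 0.51 | 1.02 |
| 0.3 | 0.507 | 57.2% | 44.0% | 60.3% | 0.66 | 0.93 |
| 0.5 | 0.600 | 44.0% | 44.0% | 54.3% | 0.77 | 0.77 |
| 0.7 | 0.775 | 28.9% | 44.0% | 49.3% | 0.87 | 0.52 |
| 0.9 | 1.342 | 12.8% | 44.0% | 45.1% | 0.97 | 0.19 |

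**Smaller groups.** For the "groups of 15 adults, toddlers, and younger children", about 13 remain after 10% dropout. The fold-rise t-test then has 23.3%, and the adjusted comparison 31.8%, 28.3% or 25.5% at r = 0.3, 0.5 or 0.7.

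**Sensitivity.**
- If 0.6 is the SD of titre, power at r = 0.3, 0.5, 0.7 is 33.4%, 44.0%, 64.6% (fold rise), 44.0% throughout (GMT) and 46.7%, 54.3%, 70.8% (adjusted).
- With unequal SDs, the variance relative to fold rise, before the 1.02, is (1 − r²)/(1 + k² − 2rk), where k = SD baseline/SD post-dose. At k = 0.5 it is 0.96, 1.00 and 0.93 for the same r, so the gain over fold rise largely disappears.
- Adjustment loses to the GMT t-test when (1 − r²) × 1.02 > 1, that is, below r = 0.14. If 10% or 20% lack a baseline, the break-even r is 0.35 or 0.47.

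**The case against.** The strongest reply is that this is a preference. A t-test on log titre or log fold rise is valid and standard, Section 6.8 calls the comparisons exploratory, and GMT and fold rise are separately listed secondary endpoints. That stands: nothing here makes the planned tests wrong.

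Three more objections also stand.
- Fold rise already uses baseline, so calling it unadjusted would be inaccurate; the point is that its slope is fixed.
- Adjustment has a price: one degree of freedom, the loss from the model of anyone without a baseline, and a common linear slope that values set to half the LLoQ can strain.
- In Parts B to D each cohort randomises one vaccine arm against placebo and cohorts enrol in sequence (Sections 4.3 and 4.4.2). Dose-versus-dose and dmLT contrasts there compare groups never randomised to each other, so baseline differences are not purely chance.

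The imbalance is also smaller against placebo, since the shells pool it within an age group. In Part B that is 6 × 10 = 60 children, and with baseline SD 0.5 the SE is 0.5 × √(1/15 + 1/60) = 0.144, or 1.4-fold.

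The missing fold-rise ratio and CI could be supplied without any model. That is true, but doing only that would leave two estimates with no rule between them.

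**Conclusion.** A worthwhile, low-cost improvement. What holds without assumption is that the two planned comparisons can differ by the baseline ratio, and that the fold-rise tables carry no ratio or CI. The precision gain is conditional. At r = 0.3 to 0.7, with equal SDs and 0.6 as the SD of log10 fold rise, power at 27 per group is about 60% to 49%, against 44% for fold rise and 57% to 29% for GMT. It shrinks to about one point over fold rise at r = 0.9, and is slightly negative against GMT below r of about 0.14.

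A reader might infer more than the document supports:
- **That every participant has a baseline.** Section 6.3.4 guarantees this for the PP population only; Section 6.3.3 does not for FA.
- **That adjustment makes the sequential dose cohorts comparable.** It does not remove cohort or calendar-time differences.
- **That it repairs the 73% power in Section 5.** It comes near that figure only in favourable cases, such as r near 0 under the first reading of 0.6. The discrepancy is a separate matter.

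**What to change.** In Sections 8.1.2–8.1.3, 8.2.2–8.2.3 and 8.3.2–8.3.3, make the PP between-arm comparison, within each age group and for each antigen, specimen and post-dose visit, a linear model of log10 post-dose titre on arm and log10 baseline titre. Report the adjusted GMT ratio with 95% CI for each planned contrast. It is identical to the adjusted GMFR ratio, because subtracting log baseline from the outcome leaves the arm coefficient unchanged. Apply the planned Holm correction to these p-values.

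Keep the unadjusted GMT and fold-rise results, with their Wilcoxon fallback, as supportive, including for FA participants without a baseline. Leave the post-dose-1 to post-dose-2 fold rise as planned, since it is not a baseline contrast. Age need not enter the model. Amend Section 6.4 to name log baseline titre as the one covariate, and state that adjusted contrasts between sequential cohorts in Parts B to D remain open to cohort and time effects.

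The cost is SAP wording, revised comparison shells and a standard model; no new data are needed.

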8.1.1 Antibody Response

Percentages of participants with an antibody response at Day 7, Day 19 or at any time point will be calculated along with the corresponding two-sided exact (Clopper-Pearson) binomial 95% CIs. For each antigen, the proportion of participants with an antibody response at Day 7, Day 19 or at any time point will be compared between each pairwise comparison of ETVAX dose level, ETVAX + dmLT dose level, and placebo using Fisher's exact test.

Tables 14.2.1.1 (a)(b)(c)(d) - 14.2.1.2 (a)(b)(c)(d) will summarize the antibody response and 95% CIs for each time period and treatment group by antigen for the FA population and the PP population, respectively. In addition, a Fisher's exact test for each treatment group comparison will be presented for each time period and antigen as shown in Tables 14.2.2.1 (a)(b)(c)(d) - 14.2.2.2(a)(b)(c)(d) for the FA population and the PP population, respectively.

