	Placebo vs ETVAX 1/4 Dose	0.xxxx	0.xxxx	0.xxxx				
	Placebo vs ETVAX # mL + 5 μg dmLT	0.xxxx	0.xxxx	0.xxxx				
	Placebo vs ETVAX # mL + 2.5 μg dmLT	0.xxxx	0.xxxx	0.xxxx				
	Combined Treatment Comparisons							
	Combined ETVAX without dmLT vs Combined ETVAX with dmLT	0.xxxx	0.xxxx	0.xxxx				
	Placebo vs Combined ETVAX without dmLT	0.xxxx	0.xxxx	0.xxxx				
	Placebo vs Combined ETVAX with dmLT	0.xxxx	0.xxxx	0.xxxx				

^{*} Using Holm's-Bonferroni adjustment within each antigen, the p-value is statistically significant.

Programming Note: Continue Table 14.2.7.1(c) for each antigen in the following order: CFA/I, CS3, CS6, CS5, and 078 LPT. For each antigen, the Holm's-Bonferroni correction will be performed. If a p-value is statistically significant after the adjustment, a "*" will be placed next to the p-value.

TABLE 14.2.6.1(d): Comparison of Geometric Fold Rise in IgA Titer by Antibody Lymphocyte Secretion - Infants (6 - 11 Months) Full Analysis Population

		P-value from t-test					
Antigen	Comparison	Baseline to Post Dose 1	Baseline to Post Dose 2	Baseline to Any Timepoint			
	Comparing Different Doses of ETVAX without dmLT						
	ETVAX 1/2 Dose vs ETVAX 1/4 Dose	0.xxxx	0.xxxx	0.xxxx			
	ETVAX 1/2 Dose vs ETVAX 1/8 Dose	0.xxxx	0.xxxx	0.xxxx			
	ETVAX 1/4 Dose vs ETVAX 1/8 Dose	0.xxxx	0.xxxx	0.xxxx			
	Comparing Different Doses of ETVAX with dmLT						
	ETVAX # mL + 5 μg dmLT vs ETVAX # mL + 2.5 μg dmLT	0.xxxx	0.xxxx	0.xxxx			
	Comparing ETVAX 1/2 Dose without dmLT with ETVAX with DMLT						
	ETVAX 1/2 Dose vs ETVAX # mL + 5 μg dmLT	0.xxxx	0.xxxx	0.xxxx			
	ETVAX 1/2 Dose vs ETVAX # mL + 2.5 μg dmLT	0.xxxx	0.xxxx	0.xxxx			
	Comparing ETVAX 1/4 Dose without dmLT with ETVAX with DMLT						
LTB	ETVAX 1/4 Dose vs ETVAX # mL + 5 μg dmLT	0.xxxx	0.xxxx	0.xxxx			
	ETVAX 1/4 Dose vs ETVAX # mL + 2.5 μg dmLT	0.xxxx	0.xxxx	0.xxxx			
	Comparing ETVAX 1/8 Dose without dmLT with ETVAX with DMLT						
	ETVAX 1/8 Dose vs ETVAX # mL + 5 μg dmLT	0.xxxx	0.xxxx	0.xxxx			
	ETVAX 1/8 Dose vs ETVAX # mL + 2.5 μg dmLT	0.xxxx	0.xxxx	0.xxxx			
	Comparing Placebo to ETVAX with and without dmLT						
	Placebo vs ETVAX 1/2 Dose	0.xxxx	0.xxxx	0.xxxx			
	Placebo vs ETVAX 1/4 Dose	0.xxxx	0.xxxx	0.xxxx			
	Placebo vs ETVAX 1/8 Dose	0.xxxx	0.xxxx	0.xxxx			
	Placebo vs ETVAX # mL + 5 μg dmLT	0.xxxx	0.xxxx	0.xxxx			
	Placebo vs ETVAX # mL + 2.5 μg dmLT	0.xxxx	0.xxxx	0.xxxx			
	Combined Treatment Comparisons						

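### Between-group GMFR contrasts, the only immunogenicity comparison with a power statement, are reported as p-values without a ratio or confidence interval

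*SAP*

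**What the plan says.** Table numbers here are those of the Appendix I shells; the text of Section 8 numbers several of these tables differently.

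- **GMFR, each arm.** Section 8.1.3: "The number of observations, GMFR and 95% confidence intervals for the GMFR will be reported".
- **GMFR, between arms.** The same section: "the p-value from a t-test for each treatment group comparison will be presented for each time period and antigen". Sections 8.2.3 and 8.3.3 match it. The infant ALS shell, Table 14.2.6.1(d), has columns headed "P-value from t-test" and nothing for the effect. Tables 14.2.12, 14.2.18 and 14.2.24 reuse that layout.
- **Responders, between arms.** Section 8.1.1: "a Fisher's exact test for each treatment group comparison will be presented for each time period and antigen". Sections 8.2.1 and 8.3.1 follow. Each arm gets an exact CI, but no contrast does.
- **GMT, between arms.** Section 8.1.2: "The mean difference and the corresponding CI limits will then be exponentiated to obtain the GMT ratio and the corresponding CI". The GMT shells carry the ratio and its CI.
- **Power.** Section 5 opens: "The sample size for this study was selected to detect frequent adverse events". For infants it then adds "approximately 73% power to detect as low as a 2-fold difference in geometric mean fold rise".

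**The concern.** The one immunogenicity effect that the plan sizes is a ratio of two GMFRs. That ratio and its interval stand in no planned comparison table. A p-value tests a ratio of 1 and says nothing directly about a ratio of 2.

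Assessing the dmLT adjuvant effect is a secondary objective, and the plan calls its immunogenicity comparisons exploratory and hypothesis generating. In that setting the size of an effect and its precision are more useful than a test. Holm correction runs over 18 GMFR contrasts per antigen and period in infants and 24 in toddlers (13 in young children, 3 in adults). Where a contrast is not significant, the comparison table will not show whether the data argue against a worthwhile adjuvant effect or are too sparse to tell.

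The planned GMT ratios do not fill the gap. They compare post-dose titres without regard to baseline. In the child parts, each vaccine regimen sits in its own stepwise cohort and is randomised only against placebo (Sections 4.3 and 4.4.2), so baseline titres may differ between the regimens compared.

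**Working it through.** **Inputs.** From Section 5: 2-fold target, log10(2) = 0.3010; log10 SD 0.6 (CS6, earlier Swedish study); two-sided 5% t-test; 30 infants per group; 10% drop-out, so 30 × 0.9 = 27 evaluable. From Sections 4.4.2 and 8: ETVAX alone pools D1–D3, 3 × 30 = 90, or 81 evaluable; ETVAX + dmLT pools D4–D5, 2 × 30 = 60, or 54 evaluable.

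**1. The plan's own figure.** SE = 0.6 × √(2/27) = 0.1633, and 0.3010 / 0.1633 = 1.843. Normal approximation: Φ(1.843 − 1.960) = 45.4%. Noncentral t: 44.0%. With 30 per group and no drop-out: 49.3% and 48.0%. The stated 73% does not follow from these inputs. It appears with about 54 per group (t, 73.3%), or with SD 0.6/√2 = 0.424 at 27 per group (t, 72.5%). That is a separate matter, but it means single-cohort contrasts are less sensitive than a reader of Section 5 would assume.

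**2. Interval for a GMFR ratio.** The 95% CI runs from ratio ÷ F to ratio × F, where F = 10^(t × 0.6 × √(1/n1 + 1/n2)) and t is the 97.5% quantile on n1 + n2 − 2 degrees of freedom.

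| Infant contrast | F | Observed 1.0 | Observed 2.0 |
|---|---|---|---|
| Single cohorts, 27 v 27 | 2.13 | 0.47 to 2.13 | 0.94 to 4.25 |
| Combined arms, 81 v 54 | 1.62 | 0.62 to 1.62 | 1.24 to 3.23 |

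For two single cohorts, 2-fold is excluded only if the observed ratio is below 2/2.13 = 0.94. For the combined arms it is excluded below 1.24.

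**3. Sensitivity to the SD.** At 27 v 27, F is 1.65 at SD 0.4, 1.88 at 0.5, 2.13 at 0.6 and 2.41 at 0.7. A single-cohort interval around 1.0 therefore excludes 2-fold only if the SD is below 0.3010 / (2.007 × 0.2722) = 0.55. For the combined arms at SD 0.7, F = 1.616^(0.7/0.6) = 1.75, still below 2.

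**4. Responders, with invented counts.** For 10/15 v 6/15, Fisher's exact p = 0.27, while the Newcombe 95% CI for the difference is −8 to +54 percentage points. The p-value alone hides that width.

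**The case against.** The strongest reply is that little is lost. Each arm's GMFR and t-based CI are tabulated, including the combined arms, so a reader can divide two numbers and rebuild an interval. In one simulated pair of arms of 27, rebuilding from values rounded to one decimal gave 2.19 (1.13 to 4.27), against 2.20 (1.13 to 4.28) from the raw data. Post-dose GMT ratios with CIs are also planned. The endpoints are secondary, no decision rule hangs on these tables, and no result would change.

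Much of that stands. But the rebuilding used the true n of 27. The GMFR shells define n as participants with an antibody response, not participants with fold-rise data, so the degrees of freedom and pooling weights would be unclear. Nor should readers have to rebuild up to 24 contrasts per antigen and period by hand. The GMT ratios leave out baseline.

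It also stands that, at SD 0.6, an interval would not settle the 2-fold question for two single infant cohorts. Precision is the limit there, and the interval only makes that visible.

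**Conclusion.** The point holds as a reporting gap. GMFR is the only immunogenicity endpoint with a power statement, and its between-group comparison is planned without the ratio or interval that GMT receives. The gain is largest for the combined infant contrast, where F is about 1.62 and an observed ratio of 1.0 would exclude a 2-fold effect.

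These figures assume that the CS6 SD of 0.6 carries over to other antigens and assays and to Bangladeshi infants, that all planned infants are enrolled, and that 10% drop out. The combined contrast also pools several ETVAX dose levels on the no-dmLT side, so its ratio is not a pure adjuvant effect.

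A reader might infer more than the document supports:

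- *That the infant sample size rests on GMFR.* Section 5 says it was chosen to detect adverse events; the GMFR power is an added statement.
- *That the trial cannot tell whether a 2-fold effect is present or excluded.* The arm-level estimates allow an approximate answer; the plan does not report it.
- *That most of the p-values will be non-significant.* The SAP gives no expected effects from which to forecast that, and many contrasts are against placebo.

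**What to change.** - In Tables 14.2.6, 14.2.12, 14.2.18 and 14.2.24, add for every contrast and period the ratio of GMFRs with a t-based 95% CI, by the method of Section 8.1.2. Give priority to combined ETVAX + dmLT v combined ETVAX alone. State that the intervals are not adjusted for multiplicity, since the Holm flags are. Amend Sections 8.1.3, 8.2.3 and 8.3.3 to match.
- In the GMFR shells, redefine n as the number of participants with fold-rise data for that antigen and period.
- In the responder comparison tables (14.2.1.3, 14.2.7.3, 14.2.13.3 and 14.2.19.3), add the difference in proportions with a 95% CI, Newcombe or exact, and name the method.

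Cost: ratio and CI columns for three periods (four for fecal), from quantities the t-test already uses; difference and CI columns beside each of the responder p-values; and one new calculation, because Fisher's test yields no interval for a difference. No new data and no change of design.
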